# 6.10 Nonpharmacologic Treatments and Procedures

Nonpharmacologic treatments and procedures (e.g., surgical, diagnostic) that occur during the study will be entered into the eCRF, including the date and reason for the treatment/procedure.

# 6.11 Assessment of Clinical Signs and Symptoms of CABP

Clinical signs and symptoms of CABP will be assessed at the time points specified in Table 1. Signs and symptoms are not obtained at TOC or LFU if the subject previously had an IACR of Failure.

The intensity of each symptom (dyspnea, cough, sputum production, and chest pain) will be evaluated and recorded as absent, mild, moderate or severe based on the definitions in Table 4 below. While Inpatient, all subjects will have clinical signs and symptom of CABP assessed daily.

Subjects who are discharged to home will be contacted by phone to assess signs and symptoms of CABP daily while on study drug with the following exception:

All subjects must have a study site visit  $96 \pm 24$  hours after the first dose of study drug to assess CABP signs and symptoms. Study personnel will inform Outpatients as to the timing of this required study site visit (see Section 6.1.1).

Table 4. Definitions of Symptom Intens
----------------------------------------

Symptom	Absent (0)	Mild (1)	Moderate (2)	Severe (3)
Dyspnea	Resolution (to pre-CABP baseline) or absence of dyspnea	Dyspnea on exertion (e.g., climbing stairs)	Dyspnea with normal/routine activities (e.g., walking)	Dyspnea at rest or requiring oxygen therapy
Cough	Resolution (to pre-CABP baseline) or absence of cough	Transient, does not interfere with normal activity	Frequent, interferes with normal activity or sleep	Constant, interferes with most or all activity or sleep
Production of purulent sputum	Resolution (to pre-CABP baseline) or absence of sputum production	Sputum production rarely causes difficulty or distress	Sputum production often causes difficulty or distress	Constant difficulty with sputum production
Chest pain	Resolution or absence of chest pain related to CABP	Transient, does not interfere with normal activity	Frequent, interferes with normal activity or sleep	Constant, interferes with most or all activity or sleep

The assessment of the clinical signs and symptoms of CABP will be used to determine ECR which will be calculated **programmatically**. The decision to maintain a subject on study drug therapy will be made by the Investigator, based on all available data and his or her best clinical judgment.

Subjects will be programmatically defined as a **Responder** if the following 4 criteria are met:

- Alive.
- Improvement in at least 2 of the 4 cardinal symptoms of CABP the subject presented with at Baseline. Improvement is defined as a decrease by at least 1 level of severity.
- No worsening of any of the 4 cardinal symptoms of CABP. Worsening is defined as an increase by at least 1 level of severity of any symptom.
- Did not receive a concomitant antibiotic for the treatment of CABP.

Subjects will be programmatically defined as a **Non-Responder** if any of the following criteria are met:

- Did not show an improvement in at least 2 of the 4 cardinal symptoms of CABP the subject presented with at Baseline. Improvement is defined as a decrease by at least 1 level in severity; or
- Worsening of any of the 4 cardinal symptoms of CABP. Worsening is defined as an increase by at least 1 level in severity for any symptom; or
- Received a concomitant antibiotic for the treatment of CABP; or
- Died from any cause.

Subjects will be programmatically defined as an **Indeterminate** if the following criterion is met:

• The symptom data are missing such that a response or non-response cannot be determined.

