#### 4 STUDY POPULATION

#### 4.1 Inclusion Criteria

Each subject must:

- 1. Be male or female  $\geq$  18 years of age.
- 2. Provide written informed consent and be willing and able to adhere to the study-specified procedures and restrictions. NOTE: Consent may be provided by the subject's legally authorized representative in accordance with local regulations.

- 3. Have an acute illness ( $\leq 7$  days duration) with at least 3 of the following symptoms consistent with a lower respiratory tract infection (new or worsening):
  - Dyspnea.
  - New or increased cough.
  - Purulent sputum production.
  - Chest pain due to pneumonia.
- 4. Have at least 2 of the following vital sign abnormalities:
  - Fever (body temperature > 38.0 °C (100.4 °F) measured orally or equivalent temperature from an alternate body site) or hypothermia (body temperature < 35.0 °C (95.0 °F) measured orally or equivalent temperature from an alternate body site).
  - Hypotension (systolic blood pressure < 90 mmHg).
  - Tachycardia (heart rate > 100 beats/min).
  - Tachypnea (respiratory rate > 20 breaths/min).
- 5. Have at least 1 other clinical sign or laboratory finding of CABP:
  - Hypoxemia (i.e., O2 saturation < 90 % on room air or while receiving supplemental oxygen at subject's baseline requirement or PaO2 < 60 mmHg).
  - Auscultatory and/or percussion findings consistent with pneumonia (e.g., crackles, egophony, dullness).
  - White blood cell (WBC) count > 10 000 cells/mm^3 or < 4 500 cells/mm^3 or > 15 % immature neutrophils (bands) regardless of total WBC count.
- 6. Have radiographically-documented pneumonia within 48 hours before enrollment (i.e., infiltrates in a lobar or multilobar distribution or diffuse opacities on chest x-ray or chest computed tomography scan consistent with acute bacterial pneumonia).
- 7. Have a Pneumonia Outcomes Research Team (PORT) Risk Class of II, III, or IV and be an appropriate candidate for oral antibiotic therapy as treatment for the current episode of CABP.
- 8. If female, meets the following criteria:

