# 6.5 Vital Signs and Oxygen Saturation

Vital signs (HR, BP, respiratory rate and body temperature) and oxygen saturation will be recorded at time points specified in Table 1. Blood pressure and heart rate assessments will be performed according to standard practice at the clinical sites. Vital signs associated with the highest temperature after the first dose of study drug will be recorded in the eCRF.

In addition, if the subject is receiving supplemental oxygen therapy, the amount given will be recorded in the eCRF.

All subjects will have vital signs and O2 saturation evaluated at Screening/Baseline and Day 1. If screening/baseline and Day 1 occur on the same calendar day, vital signs and O2 saturation do not need to be repeated. All subjects will also have assessments at EOT and TOC; at LFU, vital signs should be performed if medically indicated. If EOT and the last day of study drug are the same day, vital signs do not need to be repeated, they may be recorded once on that day (i.e., as part of the EOT assessment).

For Inpatients, in addition to the above time points, vital signs and O2 saturation will be measured daily and recorded. If multiple vital signs are taken on a study day, the highest

temperature and the vital signs associated with that high temperature will be recorded. For Outpatients, in addition to the above time points, vital signs and saturation will be measured at the study visit scheduled  $96 \pm 24$  hour after the first dose of study drug (see Section 6.1.1).

Vital signs measurements are to be repeated if clinically significant changes or machine errors occur. Out of range BP and HR will be repeated at the Investigator's discretion. Semi-supine BP and HR will be measured more frequently if warranted by the clinical condition of the subject.

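### The Severe dyspnea level counts oxygen therapy without reference to the subject's usual oxygen, so the early clinical response (ECR) score of a recovered subject on chronic oxygen depends on how the assessor reads the table

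*Protocol*

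**What the plan says.** Protocol section 6.11, Table 4, grades each cardinal symptom from 0 to 3. For dyspnea, Absent (0) is "Resolution (to pre-CABP baseline) or absence of dyspnea" and Severe (3) is "Dyspnea at rest or requiring oxygen therapy". SAP section 6.1, Table 2, repeats both cells unchanged.

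Inclusion criterion 5 (protocol section 4.1) accepts low oxygen saturation measured "while receiving supplemental oxygen at subject's baseline requirement" as one form of hypoxemia, so the plan foresees subjects who use oxygen before the pneumonia. No exclusion criterion names chronic oxygen use. Protocol section 6.5 adds that "if the subject is receiving supplemental oxygen therapy, the amount given will be recorded in the eCRF", but neither document links that record to the dyspnea score.

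The scores feed the FDA primary endpoint: "The assessment of the clinical signs and symptoms of CABP will be used to determine ECR which will be calculated" by program. A responder needs "Improvement in at least 2 of the 4 cardinal symptoms of CABP the subject presented with at Baseline" and no worsening, where "Worsening is defined as an increase by at least 1 level of severity of any symptom".

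**The concern.** The bottom of the scale is measured against the subject's usual state and the top is not. The entry criteria recognise that oxygen must be judged against the usual requirement, but that qualifier was not carried into the endpoint scale. A subject on long-term oxygen whose pneumonia dyspnea has resolved can therefore be placed at opposite ends of the scale by two careful assessors.

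The program combines the recorded levels, so it cannot correct a level that reflects background oxygen. The same scores also enter ECR in the microITT set and ECR plus vital signs. The sensitivity analyses in SAP section 8.5.2 deal with strata, indeterminate responses and short exposure; none would reveal this error. At stake is some misclassification of recovered subjects as non-responders, which lowers the observed rate and slightly dilutes any true difference between arms.

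**Working it through.** **The plan's own figure.** Inputs from protocol section 9.2 and SAP section 7.1: 79% responders in both arms, 369 per arm, margin 10 points, unpooled variance, continuity correction, one-sided alpha 0.025 as in the SAP.

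- Standard error = sqrt(2 × 0.79 × 0.21 / 369) = 0.02999.
- Continuity correction = 1/369 = 0.00271.
- Power = Φ((0.10 − 0.00271)/0.02999 − 1.960) = Φ(1.284) = 90.05%, against the stated 90%.

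The scoring question changes none of these inputs directly. It can only act through the responder rate.

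**Is there a tie-break?** Protocol sections 6.11 and 9.4.1 and SAP sections 6.1 and 7.6 contain none.

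**Effect on one subject.** Take dyspnea 3 at baseline and, at 96 hours, pre-CABP dyspnea on usual oxygen, with no other symptom worse. Scored 0, dyspnea is one of the two improvements needed. Scored 3, both must come from other symptoms. The result changes only when exactly one other symptom has improved:

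| Baseline symptoms | Patterns of the other symptoms | Patterns in which ECR changes |
|---|---|---|
| 3 (dyspnea + 2) | 4 | 2 |
| 4 (dyspnea + 3) | 8 | 3 |

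The patterns are not equally likely, so these counts are not probabilities.

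**The worsening route.** This needs baseline scored 1 or 2 by activity and the 96-hour visit scored 3 by oxygen use, in the same subject on the same oxygen. If the literal reading is used at both visits, baseline is already at the top of the scale and dyspnea cannot worsen.

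**Illustrative size for an affected subject.** Assume each symptom improves independently with probability 0.8 (not in the documents) and that usual oxygen is always scored 3.

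- Three symptoms: 0.8³ + 3 × 0.8² × 0.2 = 0.896, against 0.8² = 0.64 with dyspnea fixed. Loss 25.6 points.
- Four symptoms: 1 − 0.2⁴ − 4 × 0.8 × 0.2³ = 0.9728, against 0.896 with dyspnea fixed. Loss 7.7 points.

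**Illustrative size for the trial.** The share on chronic oxygen is not given. Assume 1% to 4%:

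- Three symptoms: 0.256 × 1% to 4% = 0.3 to 1.0 points off the overall rate.
- Four symptoms: 0.0768 × 1% to 4% = 0.1 to 0.3 points.

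A 1-point fall in both arms (79% to 78%) gives a standard error of sqrt(2 × 0.78 × 0.22 / 369) = 0.03050 and power Φ(0.09729/0.03050 − 1.960) = Φ(1.230) = 89.1%.

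Under a wider assumption (1% to 10% on chronic oxygen, 10% to 50% of them changed to non-responder, equally in both arms), the rate falls 0.1 to 5 points and power is 89.95% to 85.4%. One subject is 1/369 = 0.27 points of an arm's rate.

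**Dilution.** In the extreme case where 4% of each arm are certain non-responders whatever their true response, a true 10-point difference shrinks to 10 × 0.96 = 9.6 points.

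**The case against.** The strongest reply is grammatical. In a table that grades a symptom, the Severe cell can be read as dyspnea at rest or dyspnea requiring oxygen. On that reading a subject with no dyspnea beyond the pre-CABP state has nothing to grade, and the Absent cell settles the score. The context supports this: qualifying symptoms at entry must be new or worsening, section 6.11 concerns symptoms of CABP, and a clinician, not the program, assigns the level. This stands as a plausible reading, and it means the double classification is conditional. It does not remove the problem, because neither document states it and an assessor may reasonably take the oxygen limb on its own.

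A reader might go further and infer that every such subject becomes a non-responder through worsening. The documents do not support that: the route requires inconsistent scoring within one subject. Nor does fixing dyspnea at 3 turn every true responder into a non-responder, since two other improving symptoms are enough. The 25.6-point loss is the three-symptom case under an assumed probability and should not be quoted as the general effect. Finally, criterion 5 mentions baseline oxygen within one of three alternative findings. It shows that such subjects may enrol, not that they are common.

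**Conclusion.** Wrong as written, low impact, moderate confidence. The two dyspnea cells use different reference points, and nothing in the protocol or SAP resolves the overlap for a subject on usual oxygen, so a component of the FDA primary endpoint can be scored differently by different assessors.

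The size is unknown because the documents do not give the share on chronic oxygen. Under the assumed 1% to 4% it is at most about 1 point of the responder rate and about 1 point of power. Double-blind randomization makes the error roughly equal between arms. A reader might infer that the non-inferiority conclusion is in danger; the figures do not support that. The lower rate costs a little power and the dilution of a true difference is slight.

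**What to change.** In protocol Table 4 and SAP Table 2, qualify the oxygen limb of Severe as oxygen above the subject's pre-CABP requirement. State that a subject who has returned to pre-CABP dyspnea on usual oxygen is scored Absent (0), and that baseline and 96-hour scores follow the same rule. Notify sites before they score subjects; in any case settle the rule before unblinding.

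The cost is one phrase in each of two tables, one explanatory sentence and a site memo. No visit or procedure is added. Current oxygen is already recorded in the eCRF, and a site must know the usual requirement to apply that part of criterion 5. This is an endpoint-scoring definition only and changes no treatment decision.

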## 6.12 Investigator's Assessment of Clinical Response (IACR)

The Investigator will assess Clinical Response at time points specified in Table 1.

# 6.12.1 Investigator's Assessment of Clinical Response (IACR) at End of Treatment and Test of Cure

The Investigator's Assessment of Clinical Response will be classified as Success, Failure or Indeterminate at EOT and TOC based on the following criteria:

- **Success:** The subject's clinical signs and symptoms have resolved or improved such that no additional antibacterial therapy is administered for the treatment of the current episode of CABP.
- Failure: A subject is a treatment Failure if any of the following is met:
  - Signs and symptoms of CABP have not resolved, not improved, or have worsened such that non-study antibacterial therapy is administered for the treatment of the current episode of CABP.
  - Measures of inflammation such as temperature or elevated WBC have worsened or failed to improve such that non-study antibacterial therapy is administered for the treatment of the current episode of CABP.
  - Bacteremia has worsened or failed to improve resulting in administration of non-study antibacterial therapy.
  - The occurrence of an AE requiring discontinuation of study drug and institution of non-study antibacterial therapy for the treatment of the current episode of CABP.
  - Death from any cause.
- **Indeterminate**: Insufficient information is available to determine Success or Failure, specifically lost to follow-up.

NOTE: Subjects who have an IACR of Failure at EOT will not have an IACR assessed at TOC and will be considered to have an IACR of Failure at TOC.

## 6.12.2 Investigator's Assessment of Clinical Response (IACR) at Late Follow Up

For subjects who do not have an IACR of Failure at TOC, a determination of Clinical Response (Sustained Success, Relapse or Indeterminate) will be made at LFU based on the following criteria:

- **Sustained Success**: The subject's clinical signs and symptoms remain resolved or further improved such that no additional antibacterial therapy has been administered for the treatment of the current episode of CABP.
- **Relapse:** The subject was a Clinical Success at TOC, however, any of the following are met:
  - Clinical signs and symptoms of CABP have recurred such that additional non-study antibacterial therapy is administered for the treatment of the current episode of CABP.
  - Measures of inflammation such as temperature or elevated WBC have recurred such that additional non-study antibacterial therapy is administered for the treatment of the current episode of CABP.
  - Recurrent bacteremia resulting in administration of non-study antibacterial therapy.
  - Death from any cause.
- **Indeterminate**: Insufficient information is available to determine Sustained Success or Relapse, specifically lost to follow-up.

## 6.13 Clinical Laboratory Tests (Safety)

Safety laboratory tests will be performed at the time points specified in Table 1 and sent to a Central Laboratory. Blood samples sent to the local laboratory for the purposes of determining study eligibility must be repeated and sent to the central laboratory following enrollment. Blood and/or urine will be collected at LFU only if the subject had an abnormal (high/low flag) result at TOC. Additional tests may be performed at the discretion of the Investigator if deemed clinically appropriate. Subjects treated as outpatients must agree to return to the site for blood draws as indicated in Table 1 (i.e.,  $96 \pm 24$  hour post first dose [see Section 6.1.1], EOT, and TOC visits).

A full list of the clinical laboratory tests that will be performed and analyzed can be found in Appendix 1. A urine pregnancy test will be performed at the site on all females unless surgically sterile or at least 2 years post-menopausal. A negative urine pregnancy test is required prior to randomization. Serum must be collected on Day 1 prior to 1st dose and sent to the central lab for confirmatory testing.

Any safety laboratory results outside the normal range will be repeated at the discretion of the Investigator and will be evaluated by the Investigator or designee as "clinically significant" or "not clinically significant." Any clinically significant value should be repeated as necessary and followed until resolution.

# 6.14 Sample Collection for Pharmacokinetic Analysis

Blood samples for PK analysis of lefamulin and its main metabolite, BC-8041, will be collected in association with the first dose of study drug on Day 1 and Day 4 (see Table 5).

If PK sampling for Inpatients on Day 4 is not feasible, it can be done relative to the first dose on Day 5. For Outpatients, PK sampling will be done during the  $96 \pm 24$  hours post  $1^{st}$  dose visit. Subjects will be instructed to not take their first dose of study drug at home that day, rather to bring all blister packs (used and unused) to the study site. Following collection of the pre-dose blood sample, subjects will take their dose of study drug under supervision of study personnel, and subsequent PK blood samples will be collected.

Table 5. Sample Collection Time Points for the Determination of Lefamulin Plasma Concentrations following Oral Administration

PK Sample Time Point	Day 1 and Day 4 or 96 ± 24 hours post 1 st dose a,b
Within 1 h prior to the first dose of study drug	X
1-2 h after the first dose of study drug	X
3-4 h after the first dose of study drug	X
8-9 h after the first dose of study drug c	X

- a: Day 1 [all subjects] and Day 4 [Inpatients] or 96  $\pm$  24 hours post first dose [Outpatients]
- b: If Day 4 PK sampling for Inpatients is not feasible, it can be done relative to the morning dose on Day 5.
- c: The 8-9 h sample is required for inpatients. The 8-9 h sample is optional for outpatients; however, it should be obtained if logistically feasible.

NOTE: It is essential to record the exact time of dosing on those days when PK samples are obtained (see Section 5.7 – Adherence). Documentation of the exact blood sampling time points for population PK analysis is also essential.

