- v: Collect pleural fluid samples and/or BAL only if medically indicated. Gram's stain samples, culture, and test the isolated pathogens for susceptibility. Pathogens isolated from pleural fluid and/or BAL samples will be sent to the central laboratory for confirmatory identification and susceptibility testing. If possible, pleural fluid samples should be incubated in blood culture bottles for optimal pathogen recovery.
- w: An oropharyngeal specimen (2 swabs) and a nasopharyngeal specimen (1 swab) will be collected and frozen until sent to the central laboratory. The oropharyngeal specimen will be used for culture of *M. pneumoniae* and identification by PCR. The nasopharyngeal specimen will be used for culture and identification by PCR of *S. pneumoniae*, and potentially, *H. influenzae*.
- x: Study personnel will administer the first dose of study drug at the study site, as soon as possible after the diagnosis of CABP and completion of all required pre-dose Day 1 procedures. On Day 1, if q12h dosing is not feasible, the 1st and 2nd doses may be administered as close as 8 hours apart, in order to allow 2 doses to be given on Day 1. In this circumstance, the subject's dosing schedule should be adjusted on Day 2 to a regular q12h morning and evening schedule. Subsequently, every effort should be made to maintain a q12h dosing schedule. When this is not possible, it is acceptable to administer doses within 4 hours of the scheduled dosing time (i.e., a minimum of 8 hours between doses). For Outpatients, or in the event a subject is discharged from the hospital during the study drug administration period, an adequate supply of study drug will be dispensed for self-administration at home. Subjects will be provided instructions regarding the dosing schedule. Subjects may self-administer oral study drug at home with the following exception:

  Study personnel will advise subjects who are Outpatients that they must return to the study site to assess CABP signs and symptoms at 96 ± 24 hours after the first dose of study drug.

  See Footnote c. Administration of study drug may occur on the same calendar day as EOT, and if so will be completed before EOT assessments begin.
- y: Collect blood samples for PK analysis relative to the first dose of study drug. Blood will be collected within 1 h pre-dose, 1-2 h post dose, and 3-4 h post dose, and 8-9 h post dose.

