#### 1.5.1 Pharmacokinetics in Humans

Tissue distribution studies in healthy volunteers showed rapid lefamulin distribution achieving therapeutic exposures in relevant target tissues for the treatment of both respiratory tract and skin infections following IV and PO administration. Following a single 150 mg IV infusion, lefamulin showed higher exposure in epithelial lining fluid (ELF) as compared to the penetration into skin tissues (Zeitlinger et al., 2016). This pattern of tissue distribution has also been observed in ELF of mice. Therefore, the exposures in plasma and in ELF were used for the determination of the AUC/MIC ratio for target attainment analyses.

The plasma concentration-time curve of intravenously administered lefamulin in humans showed a multi-phasic decline. Following the end of infusion (i.e., the maximal concentration  $[C_{max}]$ ), there is a rapid distribution phase over 0.5 h followed by an extended elimination phase with a mean half-life ( $t_{1/2}$ ) of 8.6 h to 11.8 h. The major elimination route for lefamulin was non-renal. There were no statistically significant effects of age, demographics (body weight, height, or body mass index) or gender on the PK parameters of lefamulin. In addition, no significant influence of the health status on the total body clearance or drug distribution of lefamulin was observed.

Oral administered lefamulin is characterized by a plasma concentration time curve with a rapid absorption describing a bimodal peak, suggesting a mixed order absorption. The initial peak plasma concentration occurs 20-60 minutes after administration, followed by a second peak observed between 1-4 hours after dosing. Following every 12 hour intravenous infusion or oral administration, steady-state is achieved after two days and thereafter, trough levels (Cmin) remain consistently linear throughout the duration of the treatment. After oral

administration of an immediate-release (IR) tablet containing 600 mg of lefamulin, exposure — as measured by AUC (the driver of efficacy) — was equivalent to a 150 mg IV dose, the higher of 2 doses evaluated in the Phase 2 study of lefamulin in the treatment of ABSSSI (NAB-BC-3781-2001) (Wicha et al., 2013).

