# 5.4 Study Drug Treatment

The duration of blinded study drug administration will be 7 days.

Subjects randomized to lefamulin will receive oral lefamulin 600 mg q12h for 5 days (10 doses) and oral moxifloxacin placebo q24h for 7 days (7 doses). Subjects randomized to moxifloxacin will receive oral moxifloxacin 400 mg q24h for 7 days (7 doses) and oral lefamulin placebo q12h for 5 days (10 doses).

On Day 1, study personnel will administer the first dose of study drug at the study site to all subjects, as soon as possible after the diagnosis of CABP and completion of all required Day 1 procedures as outlined in Table 1. While subjects are hospitalized, all doses of study drug will be administered by hospital staff or study personnel.

For Outpatients, or in the event a subject is discharged from the hospital during the study drug administration period, an adequate supply of study drug will be dispensed for self-administration at home. Subjects will be provided instructions regarding the dosing schedule. Subjects may self-administer oral study drug at home with the following exception: Study personnel will advise subjects who are Outpatients that they must return to the study site to assess CABP signs and symptoms at  $96 \pm 24$  hours after the first dose of study drug (see Section 6.11). Study personnel will inform Outpatients as to the timing of

this required study site visit. Subjects will be advised not to take their first dose of study drug at home that day, rather to bring their blister packs (used and unused) to the study site where they will take their dose while supervised, so that specific assessments can be performed both prior to and after taking the dose (see Sections 6.4 [ECGs] and 6.14 [PK]).

On Study Day 1, if q12h dosing is not feasible, the 1st and 2nd doses may be administered as close as 8 hours apart, in order to allow 2 doses to be given on Day 1. In this circumstance, the subject's dosing schedule should be adjusted on Day 2 to a regular q12h morning and evening schedule. Subsequently, every effort should be made to maintain a q12h dosing schedule. When this is not possible, it is acceptable to administer doses within 4 hours of the scheduled dosing time (i.e., a minimum of 8 hours between doses).

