## **8.6 Pharmacokinetic Analyses**

Measured plasma concentrations of BC-3781 and BC-8041 will be summarized descriptively for the lefamulin group and nominal time point of collection. Summary statistics in the tabulation will include n, mean, standard deviation, CV [%], median, minimum and maximum.

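### The PK sample timed 8-9 h after the first dose can follow a second dose allowed from 8 h, and SAP 8.6 would still report it in the nominal 8-9 h row (minor)

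*Protocol*

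**What the plan says.** - **Sampling.** Protocol Table 5 (Section 6.14) sets four times on each PK day: within 1 h before the first dose, then 1-2 h, 3-4 h and "8-9 h after the first dose of study drug". Table 1 footnote y uses the same reference point: "Collect blood samples for PK analysis relative to the first dose of study drug". Neither places the last sample relative to the second dose. "The 8-9 h sample is required for inpatients"; for outpatients it is optional.
- **Dosing.** Lefamulin is given every 12 h. Under Protocol 5.4, if that is not feasible on Day 1, the first two "doses may be administered as close as 8 hours apart, in order to allow 2 doses to be given on Day 1". For later days, "it is acceptable to administer doses within 4 hours of the scheduled dosing time (i.e., a minimum of 8 hours between doses"). Table 1 footnote x repeats both rules.
- **Absorption.** Protocol 1.5.1 says of oral lefamulin: "The initial peak plasma concentration occurs 20-60 minutes after administration". A second peak follows at 1-4 h.
- **Analysis.** Protocol 9.9 summarizes measured concentrations by the actual time of collection. SAP 8.6 has them "summarized descriptively for the lefamulin group and nominal time point of collection". SAP 9.0, which lists changes from the protocol analyses, does not mention this one.
- **Safeguard.** Section 6.14 calls for exact dosing times on PK days and exact sampling times for the population PK analysis.

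**The concern.** The second dose becomes permissible at the moment the 8-9 h window opens. A site can follow every stated rule and still draw the sample during absorption of dose 2. The 8-9 h row is meant to show the level late in the interval after dose 1. If some of its samples sit on a second-dose peak, its mean and spread describe a mixture of two situations, and SAP 8.6 has no step to separate them.

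The situation is foreseeable. The Day 1 allowance exists so that subjects who start late can receive two doses that day, and first doses are to be given as soon as possible after diagnosis. Amendment 1 made this sample mandatory for inpatients at FDA's request, so its summary is likely to be read.

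**Working it through.** **1. The plan's own figure.** Scheduled interval 12 h minus the 4 h tolerance = 8 h. This matches the minimum stated in Protocol 5.4 and equals the start of the 8-9 h window.

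**2. A compliant example.** First dose 14:00, second dose 22:00 (8 h later), sample 22:40. The sample is 8 h 40 min after dose 1, inside its window. It is 40 min after dose 2, inside the 20-60 min initial peak.

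**3. How much of the window is exposed.** Let dose 2 be given d hours after dose 1, with 8 ≤ d ≤ 9. The part of the one-hour window after dose 2 is 9 - d. The part lying 20-60 min after dose 2 is 9 - (d + 1/3), or zero if that is negative.

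| Dose 2 at (h) | Window after dose 2 | Window in 20-60 min peak |
|---|---|---|
| 8.00 | 100% | 67% |
| 8.25 | 75% | 42% |
| 8.50 | 50% | 17% |
| 8.75 | 25% | 0% |
| 9.00 or later | 0% | 0% |

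**4. Range for the share of samples.** The documents give no distribution of second-dose times. Assume sample times are uniform over 8-9 h.
- Dose 2 uniform over 8-9 h: 1/2 = 50% drawn after dose 2, and (2/3)²/2 = 22% in the peak period.
- Dose 2 uniform over 8-12 h: one quarter of those figures, 12.5% and 5.6%.
- Dose 2 at 12 h: 0% and 0%.

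**5. Size for one affected sample (illustration).** Inputs: half-life 8.6-11.8 h (Protocol 1.5.1, reported after IV infusion). Assumptions: mono-exponential decline, and a second-dose contribution equal to the first-dose level at the reference time.
- Reference at 1.5 h: C(8.5)/C(1.5) = 2^(-7/8.6) = 0.57, or 2^(-7/11.8) = 0.66. Inflation (ratio + 1)/ratio = 2.76 or 2.51.
- Reference at 1 h: 2^(-7.5/8.6) = 0.55, or 2^(-7.5/11.8) = 0.64. Inflation 2.83 or 2.55.

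Both references give roughly 2.5 to 2.8.

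**6. Size for the reported mean.** The factor in step 5 applies to one sample, not to the row. If 5% of samples were affected (assumption), the mean would rise by 0.05 × 1.51 = 7.5% to 0.05 × 1.76 = 8.8%.

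**7. What other late information exists.** On Day 1, after the 3-4 h sample only the 8-9 h sample describes the decline from dose 1. If it follows dose 2, no late sample describes dose 1 alone. On Day 4 the pre-dose sample remains: with q12h dosing it falls about 11-12 h after the previous dose, and Protocol 1.5.1 puts steady state at two days.

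**The case against.** The strongest reply is that the analysis that matters already copes. Protocol 9.4.4 and 9.9 take Cmax, Cmin and AUC from population PK modelling, and 6.14 asks for exact dose and sample times. With both recorded, a sample after dose 2 is a usable observation. This largely stands. One gap remains: Section 5.7 commits staff to record times for inpatient and supervised doses, so the time of an outpatient's second dose at home rests on the general note in 6.14.

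It is also fair that plasma PK is an additional objective, that SAP 8.6 is descriptive with no test attached, and that the 8 h interval is a fallback, since 5.4 asks for every effort to keep to q12h. The Laboratory Manual and the separate population PK plan were not supplied and could set the order of draw and dose. These points lower the importance but do not repair the SAP table, which has its own stated rule and no exclusion or flag. SAP 7.5 provides by-subject listings of all clinical data, but a listing does not remove the sample from the nominal row.

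A reader might infer that the AUC and PK/PD results are corrupted, or that the 8-9 h sample is the only late information on both PK days. The documents do not support either: recorded times let the model place the sample correctly, and the Day 4 pre-dose sample also informs the end of the interval.

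**Conclusion.** The overlap is in the text and applies on both PK days. It arises only when dose 2 falls from 8 h to just under 9 h and the draw comes after it. The consequence is mainly a descriptive 8-9 h mean, SD and CV that can mix levels before and after the second dose. On Day 1 there is the further loss of the only late sample describing dose 1 alone. The mismatch between Protocol 9.9 and SAP 8.6 on actual versus nominal time stands whatever the frequency.

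The frequency is unknown. The 2.5 to 2.8 factor holds per affected sample, under the decline, half-life and second-peak assumptions shown; Protocol 1.5.1 itself describes multi-phasic decline after IV dosing. It should not be read as bias in the reported mean or in AUC. No efficacy or safety conclusion depends on this. Severity: minor.

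**What to change.** 1. **SAP 8.6:** take any sample whose recorded time is after that day's second dose out of the nominal 8-9 h summary, or show it in a separate row. Flag it in the listing, and keep it for the population PK model with its actual dose and sample times.
2. **SAP 8.6 and Protocol 9.9:** reconcile nominal with actual time, and record any departure from the protocol in SAP 9.0.
3. **Protocol Table 5, Section 5.4 and Table 1 footnotes x and y:** reconcile these on the order of the 8-9 h draw and the second dose, leaving the dosing rule as it is. A blanket instruction to draw first is not proposed here, because it could make a dose permitted at 8 h wait for the draw.

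The cost is a few sentences, with no new sample or procedure. The downside is that a few samples leave the descriptive 8-9 h row.
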